7. PHARMACODYNAMIC ANALYSES

Data from COR-001-treated patients from cohorts not exceeding the MTD will be pooled and data from all placebo patients will be pooled for the pharmacodynamic endpoint analyses.

Descriptive analyses by dose in which all placebo patients are pooled will also be conducted.

7.1 PRIMARY PHARMACODYNAMIC ANALYSIS

Endpoints:

The primary pharmacodynamic efficacy of COR-001 compared to placebo will be assessed by evaluating the following:

- Change from baseline (mean of Full Screening and Day 1 values) in hsCRP to Week 4 between treatment groups
 - The Day 29 value will be used for this analysis, reflecting at least 4 weeks of completed treatment. To ensure comparability to the post-baseline value, only the pre-dialysis Screening values will be used for the baseline.

Analysis Set:

Pharmacodynamic analysis population

Method:

Number of patients (n), mean, standard deviation (SD), median, quartiles (Q1 and Q3), minimum (min) and maximum (max) values for the observed value and change from baseline will be reported. The difference in changes (COR-001 - Placebo) will be presented. An analysis of covariance (ANCOVA) model will be used for this purpose with dose (specific active dose or placebo pooled) as a factor and baseline value as a covariate. The least square means for each dose, the least square mean differences from placebo along with the associated 95% confidence intervals (CIs) and p-values will be presented.

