1.2.3 Pharmacodynamic Endpoints

Data from COR-001-treated patients from Cohorts not exceeding the MTD will be pooled and data from all placebo patients will be pooled for the pharmacodynamic endpoint analyses. Dose-relationships will be explored by also presenting data by dose regimen (i.e., 2 mg Q2 weeks, 6 mg Q2 weeks, 20 mg Q2 weeks, and pooled placebo).

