2. STATISTICAL METHODS

2.1 GENERAL CONSIDERATIONS

Unless otherwise specified, all study-collected data will be summarized by treatment group using descriptive statistics, graphs, and/or raw data listings. Descriptive statistics for continuous variables will include number of patients (n), mean, standard deviation (SD), median, quartiles (Q1 and Q3), minimum (min) and maximum (max) values. Analysis of categorical variables will include frequency and percentage.

P-values will be rounded to three decimal places. If a p-value is less than 0.001 it will be reported as “<0.001.” If a p-value is greater than 0.999 it will be reported as “>0.999.” 95% confidence intervals will be estimated for pharmacodynamic endpoints.

For the analyses to be used for SRC, the subjects will be summarized by treatment group within each cohort. The placebo group will not be pooled.

For the final CSR report, the subjects will be summarized according to their treatment group. The placebo subjects at each cohort will be pooled into one group, and the subjects treated with COR-001 will be summarized based on the dosing regimen.

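### SAP 7.1 does not carry through the plan's own primary PD definition: SAA is analysed as secondary, and p-values go to each dose while the pooled comparison has no written model

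*SAP*

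**What the plan says.** **Endpoints.** Protocol 3.1.3 names SAA and hsCRP together as the primary PD endpoints, each as change from baseline to Week 4. SAP 1.2.3.1 lists the same two. SAP 7.1, the primary PD analysis, lists hsCRP alone. SAA to Week 4 reappears as item 2 of the secondary analyses in SAP 7.2, worded as in 1.2.3.1.

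**Comparison.** SAP 7 (and SAP 1.2.3 to the same effect) states how PD endpoints are compared: "Data from COR-001-treated patients from cohorts not exceeding the MTD will be pooled and data from all placebo patients will be pooled". It then adds: "Descriptive analyses by dose in which all placebo patients are pooled will also be conducted". The dose groups in SAP 1.2.3 are "2 mg Q2 weeks, 6 mg Q2 weeks, 20 mg Q2 weeks, and pooled placebo". SAP 2.1 says that in the final report "the subjects treated with COR-001 will be summarized based on the dosing regimen".

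**Model.** SAP 7.1 begins with "The difference in changes (COR-001 - Placebo) will be presented". The ANCOVA given for that purpose is "with dose (specific active dose or placebo pooled) as a factor and baseline value as a covariate". Its inferential output, after adjusted means by dose, is stated as: "the least square mean differences from placebo along with the associated 95% confidence intervals (CIs) and p-values will be presented". SAP 7.2 repeats the same structure.

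**Day.** For hsCRP, SAP 7.1 says: "The Day 29 value will be used for this analysis, reflecting at least 4 weeks of completed treatment".

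**The concern.** A primary analysis section should take the primary endpoints and the stated comparison and turn them into one model and one reported result per endpoint. SAP 7.1 drops one of the two endpoints. It also attaches inference to the by-dose comparisons that SAP 7 calls descriptive, while the pooled comparison that SAP 7 puts first has no model of its own.

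Two analysts could both claim to follow this SAP. One would report hsCRP and SAA as primary, each as a single pooled difference. The other would report hsCRP alone, as three dose differences with three p-values. What is at stake is which result carries the word primary, and whether a single small dose-level p-value is read as the primary PD finding. That choice should not remain open once treatment results are known.

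**Working it through.** **1. Status of SAA to Week 4, side by side**

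| Place | hsCRP to Week 4 | SAA to Week 4 |
|---|---|---|
| Protocol 3.1.3 | primary | primary |
| SAP 1.2.3.1 | primary | primary |
| SAP 7.1 | primary | absent |
| SAP 7.2, item 2 | – | secondary |

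SAP 12, the summary of changes to planned analyses, records no decision to demote SAA. Population, ANCOVA structure, covariate and outputs are the same in 7.1 and 7.2.

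**2. Comparison.** In SAP 7, pooled active versus pooled placebo comes first and by-dose is descriptive. In SAP 7.1 and 7.2 only placebo is pooled in the model, each dose is a factor level, and the CIs and p-values belong to the dose differences. No pooled term is written.

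**3. The plan's own hsCRP figure.** SAP 1.3.2 assumes a difference of 10.6, SD 17.3, 80% power and a two-sided t-test at 0.05. The effect size is 10.6/17.3 = 0.613. The t-test needs 42.8, so 43 per group, as stated. This sizes one active group against one placebo group; no per-dose calculation is given.

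**4. False-positive chance over three dose tests on hsCRP.** About 60 patients in six cohorts at 8:2 gives 48 active and 12 placebo. At Amendment 3 the cohorts were two at 2 mg, two at 6 mg and one at 20 mg, so 16/16/8 patients. The dose of Cohort 6 is not given; it is assumed to repeat one of the three, giving 24/16/8, 16/24/8 or 16/16/16.

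- Test for dose k: t = (mean_k − mean_0) / (s × √(1/n_k + 1/n_0)), with n_0 = 12, rejecting when |t| exceeds the 97.5% point on 55 degrees of freedom (60 patients − 4 groups − 1 covariate).
- The tests share the placebo group and so are correlated. For two doses of 16 patients the correlation is 16/(16 + 12) = 0.57.
- Chance of at least one p < 0.05 under no effect (2,000,000 simulations): 0.121, 0.121 and 0.119 for the three allocations. Cohorts 1–5 only (16/16/8, placebo 10, 45 degrees of freedom): 0.120.
- If the tests were independent it would be 1 − 0.95³ = 0.143, so sharing placebo lowers the figure.
- One pooled test: 0.05.

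**5. Two primary pooled tests (hsCRP and SAA), unadjusted.** With independent markers, 1 − 0.95² = 0.0975. At assumed correlations of 0.5 and 0.8 the figures are 0.091 and 0.078. The range is about 8–10%.

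**6. Day for SAA if it moves into 7.1.** SAP 2.3 analyses by protocol-planned visit, and Appendix A of the protocol puts Week 4 at Day 22. SAA is in Panel 3 (Appendix D), drawn in Weeks 1–6 on Days 1, 15 and 22 and not on Day 29. hsCRP is drawn on both Day 22 and Day 29.

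**The case against.** **SAA's place is only a label.** Largely true. A reader might infer that moving SAA changes its estimate or p-value. It does not, because 7.1 and 7.2 use the same model and the Day 29 rule is written for hsCRP only. What remains is that the SAP gives two answers on which results are primary.

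**The pooled comparison is already there.** The sentence "The difference in changes (COR-001 - Placebo) will be presented" can be read, under SAP 7, as the pooled difference. SAP 10.2 shows pooled treatment against pooled placebo at the interim, SAP 2.1 plans by-dose summaries, and the table shells are in a separate document not available here. So one cannot say that the pooled result will be missing. But the model said to serve that purpose has only a dose factor, and no pooled term follows. A reader might also infer that the pooling weights are open. They are not really: pooling the data means one active group, weighted by patients.

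**The p-values are nominal.** The plan claims no error control for them, so 12% describes how they may be read and is not a breach of a stated error rate. The only statement on multiplicity (SAP 10.2) concerns the interim.

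**Protocol 11.4.4 plans only descriptive summaries.** A reader might use this to excuse 7.1. It does not apply: its list has hsCRP and SAA only at Weeks 10–12, not at Week 4.

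**Version lag.** The SAP says it was built on Amendment 2, and a partly updated document may be how the conflict arose. The conflict is still between sections of the same SAP.

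**Day 29 against Day 22.** It is tempting to call this a defect or a source of bias. Both days are determinate and 7.1 gives its reason for Day 29, so it needs clarifying only.

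**Power.** A reader might argue for pooling on power: at the plan's effect, if equal at all doses and without covariate gain, 46% pooled (48 v 12) against 39%, 34% and 25% for doses with 24, 16 and 8 patients. That depends on equal effects across doses, which the documents do not establish. The argument here rests on the plan's own pooling statement.

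**Conclusion.** The point holds and should be fixed. SAP 7.1 conflicts with SAP 1.2.3.1 and protocol 3.1.3 on whether SAA to Week 4 is primary. SAP 7.1 and 7.2 conflict with SAP 1.2.3 and SAP 7 on which comparison carries the inference.

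The measurable part is about a 12% chance of at least one false positive across three unadjusted dose p-values on hsCRP, against 5% for one pooled test. This assumes three dose levels, 8:2 allocation, no dropout, no cohort above the MTD, common error variance, and Cohort 6 repeating a studied dose.

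No PD test gates a decision, the interim has no stopping rule, and the primary objective is safety. The harm is to interpretation of the PD results, not to patient protection or to the primary safety conclusion.

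**What to change.** Amend the SAP before unblinding and before Database Lock 1, when SAP 11 fixes the primary and secondary PD data:

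- **(a)** List SAA with hsCRP in 7.1 and delete item 2 of 7.2.
- **(b)** In 7.1 and 7.2, make the inferential comparison an ANCOVA of pooled COR-001 (cohorts not exceeding the MTD, as one patient-weighted group) versus pooled placebo, with baseline as covariate. Keep by-dose estimates and CIs, labelled descriptive.
- **(c)** State how the two primary PD tests are read: either as nominal p-values without error control, accepting the 8–10% above, or with a simple adjustment such as Holm (smaller p-value against 0.025, then the larger against 0.05).
- **(d)** State Day 22 as the SAA time point in 7.1, since no SAA sample exists on Day 29.

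The cost is SAP wording and one written model. No protocol change, sample, visit or patient is needed. The drawbacks are less emphasis on dose-specific p-values and a diluted pooled estimate if the lower doses have less effect; the descriptive by-dose estimates would show that.

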7.2 SECONDARY PHARMACODYNAMIC ANALYSES

Endpoints:

1. Change from baseline (mean of Full Screening and Day 1 values) in hsCRP to the mean of Weeks 10-12
2. Change from baseline (mean of Full Screening and Day 1 values) in SAA to Week 4 between treatment groups
3. Change from baseline (mean of Full Screening and Day 1 values) in SAA to the mean of Weeks 10-12
4. Change from baseline (mean of Full Screening and Day 1 values) in the free IL-6 to Week 4 between treatment groups
5. Change from baseline (mean of Full Screening and Day 1 values) in Hemoglobin to Week 4
6. Change from baseline (mean of Full Screening and Day 1 values) in Hemoglobin to Week 10-12
7. Change from baseline (mean of Full Screening and Day 1 values) in Hemoglobin to Week 10-12, excluding hemoglobin values following a change in the total weekly ESA dose. A change is defined as the first time when the ESA weekly dose goes up by >25% or down by >25% relative to the previous week's dose.
8. Change from baseline (weekly mean of Full Screening) in ERI to the mean of Weeks 9-12 and Weeks 10-12

- a. The Screening ERI is defined as the ERI used to qualify the patient for the study per Inclusion Criterion #14
9. Change from baseline (mean of Screening and Day 1 values) in TSAT to Week 4
10. Change from baseline (mean of Full Screening and Day 1 values) in TSAT to Weeks 10-12
11. Change from baseline (mean of Screening and Day 1 values) in the CHr to Week 4
12. Change from baseline (mean of Full Screening and Day 1 values) in the CHr to Weeks 10-12
13. Change from baseline (mean of Full Screening and Day 1 values) in serum pre-albumin to the mean of Weeks 10-12
14. Change from baseline (mean of Full Screening and Day 1 values) in serum albumin to Week 12

Analysis Set:

Pharmacodynamic analysis population

Method:

Number of patients (n), mean, standard deviation (SD), median, quartiles (Q1 and Q3), minimum (min) and maximum (max) values for the observed value and change from baseline will be reported. The difference in changes (COR-001 - Placebo) will be presented. An ANCOVA model including dose as a factor and baseline value as a covariate will be used. The least square means for each dose, the least square mean differences from placebo along with the associated 95% CIs and p-values will be presented. In addition, for change from baseline in TSAT to week 4, a shift table analysis with the categories: <20%, 20%-30%, >30% - 50%, >50% will be presented. The weekly mean of ERI will be calculated and presented for all ESAs combined based on the formula in [Section 1.2.3.2](#).

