The observational period for the study will start from informed consent and end with study completion (see [Section 4.6](#)) for the definition of study completion). Any event occurring after the defined observational period, even if collected on the CRF, may not be included in the planned statistical analysis. However, all data, including that reported after the defined observational period, will be included in the patient data listings.

For evaluations that are collected at multiple occasions prior to initiation of Study Drug, the latest evaluation will be considered the "Baseline" evaluation for analysis, unless otherwise specified.

11.3.4 *Missing Data Handling*

Unless otherwise specified, missing data will not be imputed and will be excluded from the associated analysis.

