Appendix C ESA and Parenteral Iron Dose-Adjustments

Weeks 1 - 4

- ESA doses are not to be adjusted or held during Weeks 1 through 4 unless one or more confirmed hemoglobin values (i.e., at least 2 consecutive measurements) or the patient's clinical status necessitates such due to a clear and present safety risk
- Parenteral iron doses are not to be adjusted or held during Weeks 1 through 4
- Patients not receiving parenteral iron products during Screening must not be started on these during Weeks 1 through 4
- The Medical Monitor must be contacted prior to any contemplated ESA or parenteral iron dose changes

Weeks 5 – 24

- Changes to ESA dosing must be based on hemoglobin values that have been confirmed (i.e., at least 2 consecutive measurements)
- Do not increase the dose more frequently than once every 4 weeks. The recommended dose increase at any given time is 25%
- Decreases in dose may occur more frequently than once every 4 weeks. The recommended minimum duration between dose reductions is 3 weeks
- If the hemoglobin rises rapidly (e.g., more than 1 g/dL in any 2-week period), reduce the dose by 25%. A greater reduction may be made, if rise in hemoglobin is unacceptably rapid
- The Medical Monitor must be contacted prior to any contemplated ESA dose changes that depart from the above protocol requirements and recommendations unless clinical urgency precludes this. If the Medical Monitor is not contacted in advance, please send a notification within 24 hours that an off-protocol ESA dose change was made
- Patients not receiving parenteral iron products must not be started on these during Weeks 5 through 24
- Parenteral iron doses are not to be adjusted or held during Weeks 5 through 24, unless approved by the Medical Monitor

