2.4 HANDLING OF MISSING DATA

As a general rule, missing data values are not imputed unless otherwise specified and, in presentation of categorical variables, unknown and missing data may be presented as a separate category and the denominator will include unknown or missing values as appropriate.

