10.2 INTERIM ANALYSIS

A single interim analysis will be conducted for the purpose of guiding future COR-001 clinical program activities. There are no stopping rules associated with the interim analysis and therefore no statistical adjustment for multiplicity will be made. The interim analysis will be conducted, at earliest, once all cohorts below that which exceed the MTD, excluding any expansion cohorts, have completed the study through Week 4 (or final visit, if prematurely discontinued).

The following endpoints will be assessed in the interim analysis:

- PD parameters: hsCRP, SAA, free and/or total serum IL-6, as well as, hemoglobin, TSAT, CHr, pre-albumin, and albumin
- Change in hemoglobin from screening to peak hemoglobin (defined as per subject absolute maximal hemoglobin in g/dL)
- Change from baseline (mean of Full Screening and Day 1 values) in Hemoglobin to Weeks 10-12, excluding hemoglobin values following a change in the total weekly ESA dose. A change is defined as the first time when the ESA weekly dose goes up by >25% or down by >25% relative to the previous week's dose.
- ERI
- Hemoglobin and ERI stratified by baseline ERI (<median or >=median)
- Cardiac biomarkers: Pro-NT-BNP and troponin
- MRI outcome: LVMI, LVESVI, LVEDVI, and LVEF
- Handgrip strength
- FACIT fatigue score

The summary approach for these listed endpoints will be the same as described in the SAP and will follow the specifications below for presentation in order to mask the treatment-level data:

- By masked treatment group (e.g. Treatment A, Treatment B, and etc.). Subjects receiving placebo from all cohorts will be combined as one of the treatment groups
 - Both PD analysis population and Per-Protocol analysis population will be performed on masked data
- Pooled treatment vs pooled placebo
- Pooled responder analysis defined as change from baseline in PD parameter for all patients (regardless of active vs placebo assignment) who achieve a $\geq 50\%$ reduction in hsCRP

To avoid identification of individual patients, the number of subjects, minimum, maximum values, and raw numbers for the percentages (i.e. numerator and denominator) will not be presented. Only the means, standard deviations, and percentages will be presented. The sponsor personnel will only receive the masked treatment group-level information and have no access to actual treatment-level information nor subject-level treatment information.

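### The hemoglobin endpoint that drops values after an ESA change analyses only the patients left; where the change was titration, patients are selected on the outcome and the estimate is probably pulled toward no effect

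*SAP*

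**What the plan says.** SAP 7.2 lists, as secondary endpoint 7, the change from baseline "in Hemoglobin to Week 10-12, excluding hemoglobin values following a change in the total weekly ESA dose". The triggering change is "the first time when the ESA weekly dose goes up by >25% or down by >25% relative to the previous week's dose". SAP 10.2 repeats the endpoint for the interim analysis: "in Hemoglobin to Weeks 10-12, excluding hemoglobin values following a change in the total weekly ESA dose".

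The model is the one used for all the secondary pharmacodynamic endpoints: "An ANCOVA model including dose as a factor and baseline value as a covariate will be used". Hemoglobin values between baseline and Week 10 do not enter it. On missing values, SAP 2.4 says that "missing data values are not imputed unless otherwise specified", and Protocol 11.3.4 says that "missing data will not be imputed and will be excluded from the associated analysis". Nothing specific to endpoint 7 overrides either rule.

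For Weeks 5-24, Protocol Appendix C states: "Changes to ESA dosing must be based on hemoglobin values that have been confirmed (i.e., at least 2 consecutive measurements". It recommends 25% for an increase and 25% for a reduction after a rapid rise, and it permits a larger reduction when the rise is judged too fast. In Weeks 1-4 ESA changes are restricted to safety needs.

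**The concern.** Endpoint 7 appears meant to show the hemoglobin effect undisturbed by ESA changes. It does this by deleting data and then comparing whoever still has a value in the window. Where the deletion follows from titration, the hemoglobin path that led to the ESA change also predicts the value that would have been seen at Weeks 10-12. The groups compared are then no longer the randomized groups, and a model with only baseline and dose cannot correct for that.

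The endpoint is one of those that inform program planning at the interim. There, SAP 10.2 withholds the number of subjects and the numerators and denominators, so a reader could not see how many patients had been removed or from which masked group.

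**Working it through.** **1. No planned figure to reproduce.** SAP 1.3.2 and Protocol 11.1 size the trial on hsCRP, TSAT and CHr only. No effect, SD or expected loss is given for any hemoglobin endpoint. The sizes below therefore rest on assumed inputs.

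**2. What the trigger catches.** The rule is |dose this week / dose last week − 1| > 0.25.

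- Recommended 25% step, up or down: 0.25, not flagged.
- Cut larger than 25%: flagged.
- Hold: 0/1 − 1 = −100%, flagged.
- One of three equal doses missed in a week (assumed schedule): 2/3 − 1 = −33%, flagged.
- ESA given every two weeks, doses read literally by week: an off-week is −100%, flagged. Inclusion Criterion 14 and SAP Section 6 average the dose over the interval; endpoint 7 does not say whether it does.

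**3. Which deletions depend on hemoglobin.** Cuts above 25% and holds made for titration do, through Appendix C. Missed doses need not. SAP 7.5 links hospitalization to both missed ESA doses and lower hemoglobin, which is a second route and not titration.

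**4. Size when deletion is titration-driven.** Assumed inputs: baseline 8.5-11 g/dL (the eligibility range), between-patient SD 0.6, within-patient SD 0.45, slope SD 0.5, Week 12 gain 1.0 g/dL, no ESA effect on hemoglobin. ESA changes from Week 5 on two values above a limit of 11-12 or below one of 9-9.5, or on a rise over 1 g/dL in 2 weeks.

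| Share of hemoglobin-driven steps flagged | True difference | ANCOVA on those left | Shortfall |
|---|---|---|---|
| All | 0.92 | 0.71 | 0.21/0.92 = 23% |
| Half | 0.92 | 0.87 | 0.05/0.92 = 5% |
| One fifth | 0.92 | 0.90 | 0.02/0.92 = 2% |

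With every step flagged, other inputs move the figure. Varying the limits gave 0.68 to 0.79 against 0.91 (13% to 25%). A second set (drift SD 0.8, visit noise 0.4, limits 9.0 and 11.5, true effect 0.70) gave 0.43, a shortfall of 0.27/0.70 = 39%; varying its inputs gave 0.27 to 0.56, or about 60% to 20%.

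**5. Other triggers, second set of inputs, true effect 0.70 before any hospitalization drop.**

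- Every step exactly 25%: nothing deleted, and endpoint 7 equals endpoint 6 (0.51 each). That shortfall comes from the ESA steps, not from deletion.
- Missed doses unrelated to hemoglobin, 30% per arm: 0.70, no bias.
- Hospitalization with a 1 g/dL drop as the only trigger, 10% placebo and 30% active: 0.66 against 0.50, overstated by about 30%. With 30% placebo and 10% active: 0.74 against 0.89, understated by 0.15/0.89 = 17%.
- No true effect, titration-driven deletion only: bias about 0.

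**6. Planned size.** About 60 patients at 8:2 is 48 active and 12 placebo. Under the second set with every step flagged, about 35 active and 8 placebo remain. Power at 0.70 g/dL is 33% for endpoint 7, 60% for endpoint 6 and 70% if no ESA were changed.

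**7. Can a model repair it?** Hemoglobin is scheduled at 11 post-baseline visits through Week 12 (Appendix A, Days 8 to 78).

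- Unstructured covariance: 11 × 12 / 2 = 66 parameters for about 60 patients, too many.
- AR(1) alone, first set of inputs, every step flagged: 0.71 to 0.86 against 0.92, still biased.
- Random intercept and slope at 48:12: 0.96 against a true 0.94, where the ANCOVA gave 0.74 (116 replicates, some with convergence warnings).
- Trigger left as it is, half the steps flagged, ESA response 0.15 g/dL per week: a missing-at-random analysis returned 0.56 against 0.70, because values after unflagged steps stay in. With every step flagged it returned 0.69.

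**The case against.** The strongest objection is that the rule may delete little. The recommended Appendix C steps are 25% and the trigger is strictly greater than 25%, so titration that follows the recommendation removes nobody. This stands and is why the size cannot be fixed. It does not clear the endpoint: the larger cuts that Appendix C permits are reserved for the fastest rises, so the titration cuts that are caught are those most tied to the outcome.

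A reader might infer that endpoint 7 simply understates the drug effect, by losing the best active responders and the lowest placebo values. The documents do not support that as fact. Appendix C names a rapid rise as a reason to cut but states no high or low hemoglobin limit; the limits above are assumptions. The loss need not fall mainly on active drug: with every step flagged in the second set, 30% of placebo and 26% of active patients were lost. Missed and hospitalization-related doses can produce no bias or the opposite bias.

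The endpoint also has company: Week 4 hemoglobin while ESA is restricted (endpoint 5), all values kept (endpoint 6), ERI (endpoint 8), ESA dose (SAP 6) and peak hemoglobin (SAP 7.3). These limit the damage, but none estimates the quantity endpoint 7 seems to target. The SAP 7.5 analyses exclude further patients or data and do not address the deletion.

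**Conclusion.** The concern holds in conditional form. The deletion, the absence of a missing-data method and the ANCOVA on those left are all in the text, and Appendix C makes titration-driven deletion depend on the outcome. In that case the estimate is likely biased toward no effect: about 20-25% on the first set of assumed inputs if every hemoglobin-driven step is flagged, more if hemoglobin drifts more widely, and about 2-6% if a fifth to a half are flagged. Deletion adds no bias if steps stay at exactly 25% or missed doses are unrelated to hemoglobin. Hospitalization-related missed doses leave the direction open. Titration-driven deletion did not create an apparent effect where there was none.

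Endpoint 7 is one of 14 secondary items in a trial whose primary endpoint is the MTD, so the trial's main conclusion is not at risk. The correction is still worth making before unblinding, because the endpoint is also used at the interim.

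**What to change.** 1. State the target of endpoint 7: the Week 10-12 hemoglobin difference had no triggering ESA change occurred.
2. Analyse it with a likelihood-based repeated-measures model on all scheduled hemoglobin values up to the first flagged change, with baseline, visit, treatment and treatment-by-time. Use a parsimonious covariance such as random intercept and slope, not AR(1) alone or a full unstructured matrix. Report the Week 10-12 contrast, and name a simpler fallback in case the model does not converge.
3. Keep the current ANCOVA as a sensitivity analysis.
4. Reconcile the SAP's >25% trigger with the 25% steps in Appendix C; otherwise values after unflagged steps remain in an analysis meant to exclude them. This concerns the analysis rule, not how ESA is dosed.
5. For ESAs given less often than weekly, average the dose over the dosing interval before applying the trigger.
6. Report the percentage removed by group and by reason (titration, hold, missed dose, hospitalization). At the interim give it by masked group; SAP 10.2 allows percentages.

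The cost is SAP wording, one model and one table; no new data are needed. The model relies on values being missing at random given earlier hemoglobin, which is plausible for titration but not for hospitalization-related missed doses, so those need a separate sensitivity analysis. With about 12 placebo patients the model may converge poorly.
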